Cohorts 3 and 4: Cohort 3 and Cohort 4 will employ a dose titration scheme intended to identify an optimal dose for each patient. Cohort 3 includes additional WHO Group I patients, while Cohort 4 (PH-ILD cohort) allows only qualified WHO Group III or WHO Group V patients.

Cohort 3 will consist of two subcohorts, randomized independently within each subcohort using a 2:1 assignment ratio (bardoxolone methyl:placebo) to be administered once daily for 16 weeks:

- Cohort 3a will consist of WHO Group I connective tissue disease (CTD)-PAH patients;
- Cohort 3b will consist of WHO Group I non-CTD PAH patients.

Cohort 4 will consist of four subcohorts, randomized independently within each subcohort using a 2:1 assignment ratio (bardoxolone methyl:placebo) to be administered once daily for 16 weeks:

- Cohort 4a will consist of WHO Group III PH patients with connective tissue disease associated interstitial lung disease (CTD-ILD);
- Cohort 4b will consist of WHO Group III PH patients with idiopathic pulmonary fibrosis (IPF);
- Cohort 4c will consist of WHO Group III PH patients with nonspecific interstitial pneumonia (NSIP) or selected idiopathic interstitial pneumonia (IIP) subtypes;
- Cohort 4d will consist of WHO Group V PH patients with sarcoidosis.

Based on the variability in 6MWD change from baseline observed for the first 24 patients enrolled in each subcohort of Cohort 3 and Cohort 4, the Sponsor may choose to increase the number of patients within each subcohort to a maximum of 72 patients. For Cohort 3b, a maximum of approximately 24 patients may be enrolled from the United States.

Patients in Cohorts 3 and 4 will start at 5 mg (or placebo) and will dose escalate to 10 mg at Week 4 unless a dose-limiting toxicity (DLT) is reported (Section 7.3.1). Identification of DLTs is left to the discretion of the Investigator and may include clinically important changes from baseline in BNP, clinical signs of fluid retention, or other adverse events. Suspected DLTs should be discussed with the medical monitor prior to changing dose. If at any time the patient reports an AE that the Investigator considers to be a DLT, the Investigator may choose to decrease the patient's dose to one-half of the prior dose (e.g., 10 mg to 5 mg). Dose de-escalation can occur more than once, but dose reduction is not permitted below a dose of 2.5 mg. Dose escalation during Part 1 is permitted for all patients at Week 4 only.

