Assessment \ Study Week (Day)	Screen A ^a	Day 1 ^b	Week 1 (Phone) Day 3±1	Week 1 ^c Day 7±3	Week 2 (Phone) Day 10±1	Week 2 ^c Day 14±3	Week 3 (Phone) Day 21±3	Week 4 Day 28±3	Week 4 (Phone) Day 31±3	Week 5 (Phone) Day 38±3	Week 6 ^c Day 42±3	Week 7 (Phone) Day 49±3	Week 8 Day 56±3	Week 12 Day 84±3	Week 16 or End of Treatment Visit ^d Day 112±3	F/U ^d
Informed consent	X															
Inclusion/ exclusion	X	X ^c														
Demographics and baseline disease characteristics	X															
Concomitant medications	X	X	X	X	X	X	X	X	X	X	X	X	X	X	X	X
Medical history	X															
Height	X															
Weight in clinic	X	X		X		X		X			X		X	X	X	X
Weight at home ^f		X	X	X	X	X	X	X	X	X	X	X	X	X	X	
Dispense weight diary		X		X		X		X			X		X	X		
Collect/review weight diary			X	X	X	X	X	X	X	X	X	X	X	X	X	
ECG	X														X	X
Vital sign measurements	X	X		X		X		X			X		X	X	X	X
Physical exam/clinical worsening assessment ^g	X	X		X		X		X			X		X	X	X	X
Pregnancy test for WOCBP ^h	X	X													X	X
Study drug administration		X	-----X-----													
Dispense study drug		X						X					X	X		
Collect study drug							X						X	X	X	
Telephone contact			X		X		X		X	X		X				
Adverse event collection		X ⁱ	X	X	X	X	X	X	X	X	X	X	X	X	X	X
Clinical chemistry	X	X		X		X		X			X		X	X	X	X
BNP and NT-Pro BNP ^j	X	X		X		X		X			X		X	X	X	X
Hematology	X	X		X		X		X			X		X	X	X	X
Urinalysis and microscopy	X	X		X		X		X			X		X	X	X	X
Virus serology ^k	X															
6-min walk test	X	X ^l						X					X	X	X ^m	X
ECHO	X ⁿ															
																
Pulmonary function testing ^r	X	X						X					X	X	X	X

Assessment \ Study Week (Day)	Screen A ^a	Day 1 ^b	Week 1 (Phone) Day 3±1	Week 1 ^c Day 7±3	Week 2 (Phone) Day 10±1	Week 2 ^c Day 14±3	Week 3 (Phone) Day 21±3	Week 4 Day 28±3	Week 4 (Phone) Day 31±3	Week 5 (Phone) Day 38±3	Week 6 ^c Day 42±3	Week 7 (Phone) Day 49±3	Week 8 Day 56±3	Week 12 Day 84±3	Week 16 or End of Treatment Visit ^d Day 112±3	F/U ^d
[REDACTED]	■	■						■					■	■	■	■
Right Heart Catheterization	X															
[REDACTED]	■	■						■					■	■	■	■
[REDACTED]		■													■	
[REDACTED]	■	■													■	■
PK samples ^v								X								
[REDACTED]	■														■	
[REDACTED]	■														■	
[REDACTED]	■															
Below assessments for Cohort 4d only^z																
[REDACTED]	■														■	
[REDACTED]	■														■	
[REDACTED]	■														■	
[REDACTED]	■														■	
[REDACTED]	■														■	

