8. SELECTION AND WITHDRAWAL OF PATIENTS

8.1. Patient Inclusion Criteria

Diagnosis and main criteria for inclusion:

1. Adult male and female patients ≥ 18 to ≤ 75 years of age upon study consent;
2. BMI > 18.5 kg/m²;
3. Symptomatic pulmonary hypertension WHO Functional Class II and III;
4. WHO Group I, III, or V PH according to the following criteria:
 - a. If diagnosed with WHO Group I PAH, then one of the following subtypes:
 - i. Idiopathic or heritable PAH;
 - ii. PAH associated with connective tissue disease;
 - iii. PAH associated with simple, congenital systemic-to-pulmonary shunts at least 1 year following shunt repair;
 - iv. PAH associated with anorexigen or drug-induced toxicity;
 - v. PAH associated with human immunodeficiency virus (HIV); or
 - b. If WHO Group III PH, then primary diagnosis must be one of the following subtypes:
 - i. Connective tissue disease associated ILD (CTD-ILD);
 - ii. Idiopathic pulmonary fibrosis (IPF), according to the American Thoracic Society and European Respiratory Society (ATS/ERS) guidelines ([Raghu 2011](#));
 - iii. Nonspecific interstitial pneumonia (NSIP) or the following idiopathic interstitial pneumonia subtypes, according to the American Thoracic Society and European Respiratory Society (ATS/ERS) guidelines ([Travis 2013](#)):
 1. Respiratory bronchiolitis-associated interstitial lung disease;
 2. Desquamative interstitial pneumonia;
 3. Cryptogenic organizing pneumonia;
 4. Acute interstitial pneumonitis;
 5. Idiopathic lymphoid interstitial pneumonia;
 6. Idiopathic pleuroparenchymal fibroelastosis;
 7. Unclassifiable idiopathic interstitial pneumonia, including patients who have not had a lung biopsy; or
 - c. If WHO Group V PH, then patient must be diagnosed with sarcoidosis;

5. Had a diagnostic right heart catheterization performed and documented prior to Day 1 that confirmed a diagnosis of PH according to all the following criteria:
 - a. If diagnosed with WHO Group I PAH, then:
 - i. Mean pulmonary artery pressure ≥ 25 mm Hg (at rest);
 - ii. Pulmonary capillary wedge pressure (PCWP) ≤ 15 mm Hg;
 - iii. Pulmonary vascular resistance > 240 dyn.sec/cm⁵ or > 3 mm Hg/Liter (L)/minute;
 - b. If not diagnosed with WHO Group I PAH, then:
 - i. Mean pulmonary artery pressure ≥ 21 mm Hg (at rest);
 - ii. Pulmonary capillary wedge pressure (PCWP) ≤ 15 mm Hg;
 - iii. Pulmonary vascular resistance > 160 dyn.sec/cm⁵;
6. Has BNP level ≤ 400 pg/mL;

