9.10.32. Clinical Worsening

The Investigator or authorized designee will evaluate clinical worsening at the time points indicated in [Table 3](#) or [Table 4](#) and [Table 5](#) or [Table 6](#). If clinical worsening is suspected, further clinic evaluations may be required to document the protocol-defined (listed below) clinical worsening event (CWE).

- Death, or onset of treatment-emergent AE with a fatal outcome occurring less than or equal to 14 days after study treatment discontinuation;
- Heart-lung or lung transplant, or hospitalization for lung transplant;
- Atrial septostomy, or hospitalization for atrial septostomy;
- The patient requires the addition of any of the following medications:
 - Prostacyclin/prostacyclin analogue (intravenous, subcutaneous, oral, or inhaled) except for acute vasodilator testing during cardiac catheterization
 - Intravenous inotropes for right ventricular failure with appropriate documentation
 - Phosphodiesterase type-5 inhibitors
 - Endothelin receptor antagonist

- Riociguat
 - The combined occurrence of the events listed below. If a CWE is confirmed by these criteria, then an NT-pro BNP laboratory assessment is required on the day of the second 6MWT with the NT-Pro BNP sample obtained after 1 hour of rest:
 1. A decrease in 6MWT by at least 15% from Baseline, confirmed by two 6MWTs, on different days;
AND
 2. Increase (worsening) \geq 1 grade in WHO FC from Baseline;
AND
 3. Appearance of or worsening of signs/symptoms of right heart failure that did not respond to optimized oral diuretic therapy.

In case of clinical deterioration the Investigator must assess carefully if the deterioration of the patient's condition (e.g., worsening functional class) is related to the underlying pulmonary hypertension or can be explained by an alternative cause (e.g., transient infection, musculoskeletal disease, surgical or medical intervention other than pulmonary hypertension-related, exacerbation of a concomitant lung disease, lacking compliance of medication intake). Only persistent clinical deteriorations caused by the underlying pulmonary arterial hypertension will be considered a clinical worsening event.

Time to clinical worsening will be evaluated as the number of days between randomization and the occurrence of a predefined clinical worsening event.

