#### 1.8 Study Cohorts

As described in Section 1, this study includes 2 cohorts in the dose-ranging phase and 6 sub-cohorts (within 2 overarching cohorts) in the dose-titration phase. Analyses described in this SAP may be performed separately by cohort. The Part 1 and Part 2 safety and efficacy analyses will be summarized by randomized treatment, pooling all placebo patients and all active patients into various subgroups:

- All PAH patients (Cohorts 1, 2, 3a, and 3b patients)
- All CTD-PAH patients (CTD-PAH patients in Cohorts 1, 2, and 3a)

- All Non-CTD PAH patients (Non-CTD PAH patients in Cohorts 1, 2, and 3b)
- All PH patients (Cohorts 4a, 4b, 4c, 4d)

In addition to the subgroups listed above, the eGFR, six-minute walk test, and pulmonary function testing results will be summarized by individual cohort.

All patients enrolled in the study will follow the same schedule of assessments, including a placebo-controlled period (Part 1) followed by an extension period (Part 2).

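### The sentence that decides a clinical worsening event says pulmonary arterial hypertension, while the sentence before it says pulmonary hypertension; for Cohort 4 the two do not agree.

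*Protocol*

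**What the plan says.** Protocol 9.10.32 lists the components of a clinical worsening event: death, transplant, septostomy, the addition of certain medications, and a combined criterion. The combined criterion needs a confirmed fall in walk distance, a worse functional class and signs of right heart failure, all three together.

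A paragraph on cause follows. The investigator must judge whether a deterioration "is related to the underlying pulmonary hypertension or can be explained by an alternative cause". The examples of alternative causes include "exacerbation of a concomitant lung disease, lacking compliance of medication intake". The paragraph ends with the deciding sentence: "Only persistent clinical deteriorations caused by the underlying pulmonary arterial hypertension will be considered a clinical worsening event". Time to clinical worsening is then counted from randomization to a predefined event, with no exception for any cohort.

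On the population, Protocol 7.1 says that "Cohort 4 (PH-ILD cohort) allows only qualified WHO Group III or WHO Group V patients". Table 4, which covers Cohorts 3 and 4, has a row headed "Physical exam/clinical worsening assessment", and its footnote sends the investigator to 9.10.32 when worsening is suspected. The readable text gives no separate definition for Cohort 4.

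**The concern.** The two attribution sentences use different disease terms. In Cohorts 1 to 3 this makes no difference, because those patients have WHO Group I PAH. In Cohort 4 it does: a deterioration driven by the patient's pulmonary hypertension (PH) passes the question in the first sentence and fails the rule in the second.

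The readable text describes no central adjudication of these events, so the choice between the two sentences falls to each investigator. Two sites could classify the same Cohort 4 course differently, and time to clinical worsening in that cohort would then depend partly on which sentence a site followed.

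**Working it through.** **Step 1. Do the documents treat PAH and PH as different things?**

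- The protocol's abbreviation list has separate entries for PAH, PH and PH-ILD.
- Protocol 8.1 sets its own haemodynamic criteria under the words "If not diagnosed with WHO Group I PAH, then", and these apply to the Group III and V patients.
- SAP 1.8 labels Cohorts 1, 2, 3a and 3b as PAH patients and Cohorts 4a to 4d as PH patients.

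Where the documents define populations, PAH means WHO Group I and Cohort 4 lies outside it.

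**Step 2. Apply each sentence to a deterioration due to the patient's pulmonary hypertension.**

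| Cohort | First sentence (PH) | Deciding sentence (PAH) | Agree? |
|---|---|---|---|
| 1, 2, 3a, 3b (Group I) | Counts | Counts | Yes |
| 4a to 4d (Group III/V) | Counts | Does not count, if read literally | No |

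**Step 3. Which components are exposed?**

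- The combined criterion is the component most clearly judged by attribution. The paragraph on cause is about clinical deterioration and gives worsening functional class as its example.
- Death, transplant, septostomy and added medication are listed without a condition that PH be the cause. The text does not say whether the later sentence screens them too. If it does not, they count in Cohort 4 on either reading.

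**Step 4. How large is the affected group?** The inputs are in Protocol 7.2: 38 in Cohort 1, 16 in Cohort 2, and 24 in each of six subcohorts, which may rise to 72 each.

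- Planned total: 38 + 16 + 6 × 24 = 198, as stated. Cohort 4: 4 × 24 = 96, and 96/198 = 48.5%.
- Maximum total: 38 + 16 + 6 × 72 = 486, as stated. Cohort 4: 4 × 72 = 288, and 288/486 = 59.3%.

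**Step 5. What does one reclassified event do?** With 2:1 randomization, a subcohort of 24 has 16 active and 8 placebo patients. One event moved in or out changes the observed proportion by 1/16 = 6.25 points on active or 1/8 = 12.5 points on placebo. Pooled over Cohort 4 (64 and 32), the change is 1/64 = 1.6 or 1/32 = 3.1 points. This shows sensitivity only. The documents give no event rates, so the number of events affected cannot be estimated.

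**The case against.** The strongest reply is that this is a drafting slip. The deciding sentence refers back to the disease named just before it, and both documents use PAH loosely in text that covers Cohort 4. Footnotes to Tables 4 and 6 speak of the PAH treatment regimen. SAP 2.1 says Cohorts 3 and 4 are assigned by PAH etiology. SAP 3.4.4.1 describes the primary walk-distance effect as one in PAH patients; read just as literally, that would drop Cohort 4, yet SAP 3.4.4 plots its walk-test results. Much of this stands. Carry-over wording is the likeliest explanation, and many investigators would read through it. But the sentence in 9.10.32 decides whether an event is counted, and an operative rule should not depend on readers ignoring its wording.

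Two stronger readings are tempting, and the documents do not support them.

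- A reader might infer that no Cohort 4 patient can ever have a clinical worsening event. Four of the listed component types carry no PH-cause condition, so the literal exclusion is clear only for deteriorations judged by attribution.
- A reader might infer that naming exacerbation of lung disease as an alternative cause is itself an error, because lung disease is what qualifies Cohort 4 patients. The first sentence sets alternative causes against the underlying PH, not against the underlying illness in general. For an endpoint specific to PH, that exclusion is coherent.

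It also stands that SAP 1.8 keeps Cohort 4 apart from the PAH groups, so the problem does not reach the PAH summaries.

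**Conclusion.** The inconsistency is real, and as written the deciding sentence gives the wrong answer for Cohort 4 deteriorations judged by attribution. The likely consequence is classification that varies between investigators, rather than certain under-counting.

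A reader might take 48.5% to 59.3% to mean that the endpoint is wrong in about half of the trial. Those figures are only Cohort 4's share of enrolment. The share of events affected is unknown, and it is smaller if attribution governs only the combined criterion.

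The endpoint is not primary: the primary efficacy endpoint is change in 6MWD, and SAP 1.5.2 rests the primary objective on the totality of the data. The exploratory endpoint lists are redacted, so the rank of time to clinical worsening, and any analysis specific to Cohort 4, cannot be seen. The conclusion assumes that the redacted text holds no separate Cohort 4 definition and that PAH keeps the meaning it has in the eligibility criteria and SAP 1.8.

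**What to change.** Make two edits to the endpoint definition in Protocol 9.10.32:

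1. Reconcile the two sentences by using pulmonary hypertension in the deciding sentence as well. Cohorts 1 to 3 are unaffected.
2. State whether the attribution rule applies to every listed component or only to the combined criterion.

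An optional addition for Cohort 4 is to record the judged cause (PH, progression of ILD or sarcoidosis, other) and to report events from any cause beside those due to PH. This would show whether attribution changes the picture, but it is an extra analysis and not the correction of an error. It would need an added eCRF field and some data entry.

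The cost of the two edits is a minor wording amendment, with the approvals that Protocol 15.5 requires. Clinical worsening is also a listed reason for discontinuation in Protocol 8.4. The edits proposed here concern only how events are counted, and no change to that management text is suggested.

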8.4. Patient Withdrawal and Discontinuation

Patients have the right to withdraw from the study at any time for any reason, without prejudice to their medical care. The Investigator may discontinue a patient from the study for any of the following reasons:

- Clinical worsening;
- Occurrence of an adverse event or change in medical status that leads the Investigator or Sponsor to be concerned about the patient's welfare;
- Investigator determines the patient is non-compliant with study procedures;
- Females who become pregnant during the study;
- Failure to return for follow-up.

Patients must be withdrawn from the study if any of the following occur.

- ALT or AST > 8X ULN;
- ALT or AST > 5X ULN for 14 days;
- ALT or AST > 3X ULN and (total bilirubin > 2X ULN or INR > 1.5);
- ALT or AST > 3X ULN with the appearance of fatigue, nausea, vomiting, right upper quadrant pain or tenderness, fever, rash, and/or eosinophilia (> 5%);
- Withdrawal of consent;
- Death.

Patients who discontinue from the study will be asked to complete the end-of treatment and follow-up procedures noted in [Table 3](#) or [Table 4](#) and [Table 5](#) or [Table 6](#) depending on which cohort the patient is enrolled in and whether the patient is Part 1 or 2 of the study. Patients who complete the 16 weeks of Part 1 but choose not to participate in Part 2 (the extension period) should complete the follow-up procedures in [Table 3](#) or [Table 4](#) and [Table 5](#) or [Table 6](#). Patients should complete end-of-treatment procedures, including the 6MWT, prior to any adjustments being made to their PAH treatment regimen. Patients who discontinue for elevated transaminase levels should complete the End-of-treatment visit, the Follow-up visit **and** should also be followed per [Section 9.1.2](#) if acceptable levels are not reached at the Follow-up visit.

Every effort should be made to contact patients who do not return for a scheduled visit. The Investigator should inquire about the reason for withdrawal, request the patient return all unused investigational product(s), request the patient return for end-of-treatment and follow-up visits (if applicable), and follow-up with the patient regarding any unresolved AEs. Patients who discontinue participating in the study for any reason may not re-enter the study at any time.

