9.1.2. Management of Elevated Transaminase Levels (ALT and/or AST)

Nearly all instances of elevated transaminases are expected to be asymptomatic. Check transaminase levels (as well as total bilirubin (TBL), GGT, alkaline phosphatase (ALP), and International Normalized Ratio (INR) within 48-72 hours during an unscheduled visit if the following occurs:

- ALT or AST levels > 3X ULN

Repeat testing every 72 to 96 hours until transaminase levels are below three times the ULN for at least one week or the patient withdraws consent.

Discontinue study drug administration permanently if any of the following occurs:

- ALT or AST > 8X ULN
- ALT or AST > 5X ULN for more than 2 weeks
- ALT or AST > 3X ULN and [TBL > 2 x ULN **or** INR > 1.5]
- ALT or AST > 3X ULN with the appearance of fatigue, nausea, vomiting, right upper quadrant pain or tenderness, fever, rash, and/or eosinophilia (> 5%); The hepatobiliary tree must be visualized (e.g., ultrasound, MRI) and assessed if a patient discontinues taking study drug secondary to elevated transaminase levels. Additional tests/studies may be warranted depending on the clinical presentation.

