9.3. Concomitant Medications

9.3.1. Excluded Medications

Patients taking these medications or treatments will be ineligible for enrollment or continuation in the study:

- Any other investigational drug or device studies;
- Intravenous (iv) or subcutaneous (sc) prostacyclin/prostacyclin analogue;
- Intravenous inotropes;
- Inhaled nitric oxide (excluding acute vasodilator testing during diagnostic cardiac catheterization).

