Transient deteriorations of clinical status requiring hospitalization, treatable by, for example, short-time application of intravenous diuretics, positive inotropic agents or non-invasive ventilation and allowing patients discharge within 48 hours, are not considered to meet the criteria for a CWE. Patients should be discontinued only if any of the above criteria exceed 48 hours.

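### Protocol rules on who leaves the study disagree for short-course intravenous inotropes (9.3.1 against 9.10.32) and, at exactly 14 days, for ALT/AST above 5X ULN (8.4 against 9.1.2)

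*Protocol*

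**What the plan says.** **Inotropes.** Protocol 9.3.1 opens its list of excluded treatments with "Patients taking these medications or treatments will be ineligible for enrollment or continuation in the study". One entry is simply "Intravenous inotropes", with no duration, indication or exception. The entry for inhaled nitric oxide in the same list does carry an exception, for acute vasodilator testing.

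Protocol 9.10.32 lists among the clinical worsening events the required addition of "Intravenous inotropes for right ventricular failure with appropriate documentation". It then restricts the definition: "Only persistent clinical deteriorations caused by the underlying pulmonary arterial hypertension will be considered a clinical worsening event". Its closing paragraph says that a transient deterioration needing hospital care and treatable by, for example, "short-time application of intravenous diuretics, positive inotropic agents or non-invasive ventilation", with discharge within 48 hours, does not count as a clinical worsening event. It ends: "Patients should be discontinued only if any of the above criteria exceed 48 hours".

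**Transaminases.** Protocol 8.4 lists conditions under which a patient must be withdrawn from the study, among them "ALT or AST > 5X ULN for 14 days". Protocol 9.1.2 lists conditions under which study drug must be stopped permanently, among them "ALT or AST > 5X ULN for more than 2 weeks". The other three liver criteria match in the two sections.

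**The concern.** A site looking up what to do with one patient can find different answers in different sections, and nothing in the protocol says which section prevails. The cross-reference from 8.4 to 9.1.2 concerns follow-up after a patient has already stopped for raised transaminases. It does not align the trigger.

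The statistical interest lies in what leaving the study does to the data:

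- Under SAP 3.4.4, an end-of-treatment walk from a patient who stops early is assigned to the closest nominal visit, and later Part 1 visits are filled by LOCF. A patient who stays contributes observed walks.
- Under SAP 3.1.3, a patient with fewer than 28 doses is outside the mITT population, which is used for all 6MWD analyses.
- Under Protocol 7.1, premature discontinuation in Part 1 closes off Part 2. Under 8.4, a patient who has discontinued may not re-enter.

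If sites resolve the conflict differently, these outcomes depend partly on which section was read.

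**Working it through.** The plan gives no figure to reproduce here. The check applies each rule to the same patient.

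**Case A: a deteriorating patient given intravenous inotropes briefly and discharged within 48 hours.**

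| Source | Duration condition | Continuation | Clinical worsening event? |
|---|---|---|---|
| 9.3.1 | none | ineligible | not addressed |
| 9.10.32, inotrope bullet alone | none | not addressed | yes |
| 9.10.32, persistence sentence and closing paragraph | discharge within 48 hours | not to be discontinued | no |
| 8.4 | none | inotropes not on the mandatory list; discretion for clinical worsening or an adverse event of concern | not addressed |

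On event status, 9.10.32 read as a whole gives one answer: not an event. On continuation, 9.3.1 and the closing paragraph of 9.10.32 give opposite answers, and neither mentions the other. The closing sentence is also loose. It refers back to criteria exceeding 48 hours, but death, transplant and septostomy, listed earlier in the section, have no such duration.

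**Case B: ALT or AST above 5X ULN, no other liver criterion met.** Two weeks = 14 days.

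| Duration above 5X ULN | 8.4 (for 14 days) | 9.1.2 (more than 14 days) |
|---|---|---|
| under 14 days | not met | not met |
| exactly 14 days | met | not met |
| over 14 days | met | met |

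The retest schedule in 9.1.2 can land on day 14. The first recheck is at 48 to 72 hours (2 to 3 days), then every 72 to 96 hours (3 to 4 days). For example, 2 + 4 + 4 + 4 = 14, or 3 + 4 + 4 + 3 = 14. The next scheduled test after day 14 falls on day 14 + 3 = 17 or 14 + 4 = 18.

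The named actions also differ: 8.4 removes the patient from the study, while 9.1.2 stops the drug. In practice the gap is small, because Protocol 7.1 sends a patient who stops drug in Part 1 to an end-of-treatment visit and a follow-up visit four weeks after the last dose, and 8.4 asks for the same procedures.

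**How Case B could reach the analysis set (constructed example).** Assume one dose per day with none missed, a first value above 5X ULN at the Week 2 visit on Day 14, and each stop taking effect before that day's dose.

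- Stop at 14 elapsed days: Day 14 + 14 = Day 28, so 28 − 1 = 27 doses, below the 28 required for mITT.
- Stop at the next retest: Day 31 or 32, so 30 or 31 doses, which meets the dose requirement.

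This shows only that the boundary can matter for one patient. It says nothing about how often.

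**The case against.** **On inotropes.** The specific rule may be read over the general one: 9.3.1 concerns patients taking a listed drug, whereas 9.10.32 describes a short course that has ended by discharge. The mandatory withdrawal list in 8.4 does not include inotropes, and 9.3.2 calls for consulting the medical monitor before a patient is withdrawn. This is a reasonable way to resolve the conflict, but the protocol does not state it. Nothing limits 9.3.1 to ongoing use, and where that list was meant to have an exception, one was written in.

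Two stronger readings are tempting and should be resisted:

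- A reader might infer a three-way conflict in which the same episode also is and is not a clinical worsening event. The persistence sentence and the closing paragraph sit in the same section as the bullet and qualify it, so the documents give one answer.
- A reader might infer that 9.10.32 obliges the patient to stay. It says when patients should be discontinued, and 8.4 leaves the investigator discretion for clinical worsening or an adverse event of concern.

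**On transaminases.** Section 9.1.2 does not say that drug may be stopped only after more than two weeks, so a site that withdraws a patient at day 14 breaches neither section. Protocol 5.1.3 also reports that persistent elevations above 3X ULN had not been observed. Both points stand. They make the situation rare and the conflict narrow, but they do not explain why one safety stop is worded in two ways.

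**Conclusion.** Two inconsistencies stand in the current protocol. The firmer one concerns continuation after short-course intravenous inotropes: 9.3.1 and 9.10.32 give opposite answers for the same patient. The other is a boundary mismatch at exactly 14 days above 5X ULN, together with different named actions. The point is minor.

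No numerical effect is claimed, because the documents give no frequency for either situation. Three inferences about size are not supported:

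- In a subcohort of 24 randomized 2:1, one patient is 1/16 = 6.3% of the active arm or 1/8 = 12.5% of the placebo arm. That is the weight of any single patient, not an effect of these rules.
- The 4 to 11% above 3X ULN in Protocol 5.1.3 describes past studies. It is not a forecast for this one, and no share above 5X ULN is given.
- A further 3 to 4 days of dosing would need a retest exactly on day 14 and a site that waits under 9.1.2 without acting on 8.4.

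Much of the exploratory analysis is redacted, so the way clinical worsening is analysed cannot be judged. The conclusion rests on the wording of the four protocol sections and on the absence of any precedence rule between them.

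**What to change.** Reconcile 9.3.1 with the closing paragraph of 9.10.32, so that the two give one answer on continuation after short-course intravenous inotropes. While that paragraph is open, state which criteria its 48-hour limit refers to. Use identical wording in 8.4 and 9.1.2 for the duration above 5X ULN and for the resulting action. The sponsor decides which rule applies in each case; this review takes no position on that.

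The cost is a protocol wording amendment and a memo to sites, with no added visits, tests or patients.
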